4 PARTICIPANT ENTRY

4.1 PRE-REGISTRATION EVALUATIONS

Potential participants for this study will have received clinical evaluations as part of their oncology/cardiology treatment, such as base-line blood tests at one or more participating hospital site, a 2D echocardiogram at one or more participating hospital site, and a 3D echocardiograms at LHCH.

4.2 INCLUSION CRITERIA

4.2.1 Cardiotoxicity Cohort

- Over 16 years of age at the time of consent.
- Capable of providing informed consent as determined by the consenting clinician.
- Receiving doxorubicin chemotherapy treatment at the time of consent or previously received doxorubicin chemotherapy treatment prior to consent.
- Clinical presentation of left ventricular systolic dysfunction at the time of consent secondary to
 receiving doxorubicin chemotherapy treatment as determined by the clinical team.

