1 INTRODUCTION

1.1. BACKGROUND

Anthracyclines are amongst the most widely prescribed and effective anticancer drugs in use, and remain an important part of treatment regimes in both adult and paediatric oncology practice [1-5]. The efficacy of anthracyclines however is hindered by the significant side effects that they induce. Cancer treatment is therefore no longer aimed exclusively at treating the malignancy, but also at the early identification and treatment of the toxic side effects. One of the potentially life-threatening toxic side effects of anthracycline use is cardiac toxicity [6, 7]. The cardiotoxic potential of anthracyclines routinely used in the treatment of breast cancer and haematological malignancies for example, such as doxorubicin, specifically requires close monitoring of cardiac function [8, 9]. Doxorubicin, the most commonly prescribed anthracycline [10] is known to cause potentially irreversible cardiomyocyte death, either through necrosis or apoptosis [5]. The exact cytotoxic mechanism of anthracyclines remain unclear, with contradictory theories observed within the literature [11-21].

The severity of side effects from anthracyclines such as doxorubicin is largely dose dependent, with cumulative administered dose being the most critical factor in the development of cardiotoxicity [22]. Anthracycline-induced cardiotoxicity typically manifests as left ventricular systolic dysfunction (LVSD) and congestive heart failure [23-25] with additional risk factors for prediction including age (< 4 years and > 60 years), significant hypertension, and female gender [9, 26]. In adults, the incidence of heart failure induced by doxorubicin varies from 4% to 5% at a cumulative dose of 500-550 mg/m2, to 36% at a cumulative dose of 600 mg/m2 or more [9, 22]. The cardiotoxic side effect of anthracyclines determines their cumulative maximal tolerable dose.

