1.1.1. Categorising Cardiotoxicity

Anthracycline-induced cardiotoxicity is currently recognised clinically in three categories: acute, earlyonset chronic, and late-onset chronic [27]. Acute toxicity is directly associated with drug infusion and typically resolves spontaneously within hours [28]. Whilst acute cardiotoxicity does not represent a serious clinical problem, chronic toxicity does. Early-onset chronic anthracycline cardiotoxicity is typically observed within weeks to months of the patient receiving their final treatment, whereas lateonset chronic cardiotoxicity sees a delay period that can last up to twenty years before evidence of cardiotoxicity eventually presents. Late-onset cardiotoxicity is often a complication observed in childhood cancer survivors [29, 30]. Acute cardiotoxicity has been shown to occur in less than 1% of patients immediately after anthracycline administration whilst early-onset chronic cardiotoxicity occurs in 1.6 - 2.1% of patients within one year of therapy (with a peak incidence at three months post treatment) and late-onset chronic cardiotoxicity occurring in approximately 5% of patients more than one year post therapy [31].

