3.3 OUTCOME

Our primary outcome for this study is to generate iPSC-derived cardiomyocytes that are reproducible, amenable to experimental analysis, and that recapitulate the phenotype of the donor at the molecular and cellular level. This will not only allow us to begin addressing the research questions set out in this study of being able to better understand chemotherapy-induced cardiotoxicity, but will also enable us to use the technology to investigate other cardiac conditions and congenital defects.

Secondary outcomes include:

- Identifying a doxorubicin-specific signature in the cells derived from our cardiotoxicity subjects
 which signifies a distinct biological process that is absent in the control group. This would allow us
 a potentially significant insight into the mechanistic effects of doxorubicin-induced cardiotoxicity
 at a cellular and molecular level.
- Identifying candidate biomarkers that are of a functional relevance to doxorubicin-induced cardiotoxicity. Novel biomarker discovery could potentially offer an enhanced alternative to the current standard of risk stratification and cardiotoxicity detection in the clinic.
- Obtaining data that will support further investigations into different areas of future research such as the role of candidate biomarkers that could predict anthracycline-induced cardiotoxicity in other cancers and what their relationships are to cumulative drug dosing strategies for example.

These outcomes could eventually enable clinicians to better predict which patients will develop cardiotoxicity and how their care can be more appropriately managed. The research will deepen the understanding of doxorubicin-induced cardiotoxicity for health care professionals and service providers for integrated care. It will also assist in providing a better understanding of the options available for supporting chemotherapy patients at various stages of their care both during and following the completion of their treatment. It has the potential to improve the wellbeing and lives of patients as well as to improve how primary and secondary care services work together. The study will develop high quality data that will be disseminated with researchers, service users and health care professionals to create more effective practices in care.

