3.4 STUDY SETTING

In this multicentre study we will recruit participants from three NHS outpatient services (LHCH, CCC, RLBUHT) with the help of clinicians and staff members working across these sites. Participants will be actively identified and recruited at all sites as follows:

- Liverpool Heart and Chest Hospital will identify and recruit doxorubicin-treated chemotherapy
 patients who do or do not exhibit cardiotoxicity as determined by the appropriate clinical coinvestigator (named on page vii of this document).
- Clatterbridge Cancer Centre and the Royal Liverpool and Broadgreen University Hospitals NHS Trust will refer doxorubicin-treated chemotherapy patients to LHCH for further examination.

Version 2.24. Date: 1547/095/2022; IRAS:

Page 21 of 44

LHCH provides specialist services in cardiothoracic surgery, cardiology, respiratory medicine and diagnostic imaging across Merseyside, Cheshire, North Wales, and the Isle of Man. Its outpatient department sees an estimated 70,000 patients a year and conducts a recently introduced consultant-led cardio-oncology clinic which see approximately 30 new referrals per month.

The Clatterbridge Cancer Centre NHS Foundation Trust is one of the UK's leading cancer centres and provides specialist cancer care across Cheshire, Merseyside and the surrounding areas including the Isle of Man. The centre provides non-surgical cancer care for blood cancers and solid tumours and operates specialist chemotherapy clinics in local district hospitals, including one of our participating sites - RLBUHT. The new Clatterbridge Cancer Centre, situated in central Liverpool alongside the University of Liverpool and Royal Liverpool University Hospital, will more greatly support recruitment opportunities of non-cardiotoxicity patients should it be necessary, and increase sample processing efficiency at the neighbouring University site.

The RLBUHT oncology services are world renowned and offer treatments for most types of cancer. The hospital works in collaboration with Clatterbridge and LHCH to deliver up-to-date care for cancer patients.

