4.3 EXCLUSION CRITERIA

- Under 16 years of age at the time of consent.
- Lacking ability to provide informed consent as determined by the consenting clinician.
- Judged to have been coerced to consent as determined by the consenting clinician.
- Pre-existing left ventricular systolic dysfunction to be reviewed by the clinical team on a case-by-
- case basis.
- Recent surgery (<3 months).
- Excessive alcohol consumption (>30 units a week) and/or recreational drug use.
- Active immunological disease as determined by the clinical team.
- On current steroid therapy with the exception of corticosteroid inhaler <2mg/kg.
- Active or recent (<6 weeks) serious infection as determined by the consenting clinician.
- Inability to comply with study procedures.

Version 2.24. Date: 1517/095/2022; IRAS:

Page 27 of 44

Formatted: Body Text, Space Before: 0 pt, No bullets or numbering, Tab stops: Not at 1.45 cm + 1.45 cm

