6.2.2.1 Cell lines

All cell lines used in this study will be generated from somatic patient cells. The cells used for reprogramming will be PBMCs isolated and cultured from whole blood. Cells will be reprogrammed using either Sendai-virus transduction or by electroporation of episomal plasmid vectors. Cell lines

Version 2.24. Date: 1547/095/2022; IRAS:

Page 29 of 44

generated will be allocated a pseudoanonymised form of identification by the research staff at the University of Liverpool. Surplus primary material (PBMC) will be cryopreserved in cryopreservation medium. Cells will be frozen in isopropanol containers at -80°C for 24 hours before being transferred to long-term storage at -150°C under HTA guidelines. All samples will be stored at the University of Liverpool.

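### Sections 4.2–4.3 do not exclude prior allogeneic stem-cell transplant, yet every line is made from blood cells and no line is checked against the participant's own genotype

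*Protocol*

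**What the plan says.** Sections 4.2.1 and 4.2.2 of the Protocol share one treatment criterion: "Receiving doxorubicin chemotherapy treatment at the time of consent or previously received doxorubicin chemotherapy treatment prior to consent". Neither limits tumour type. Section 4.3 covers age, consent, pre-existing ventricular dysfunction, recent surgery, alcohol and drugs, steroids, infection, compliance, and "Active immunological disease as determined by the clinical team". It does not mention transplant or circulating blood cancer.

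Section 6.2.2.1 states "All cell lines used in this study will be generated from somatic patient cells" and then "The cells used for reprogramming will be PBMCs isolated and cultured from whole blood". No second tissue is collected. The stored material in section 3.6.5 (mononuclear cells, plasma, nucleic acids) comes from participant samples, and the only sample taken is blood.

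The primary outcome in section 3.3 needs cells that "recapitulate the phenotype of the donor at the molecular and cellular level". Section 6.2.2.7 then compares protein expression between cardiotoxicity and non-cardiotoxicity samples with a two-tailed t test.

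Blood cancers appear in two places. Section 1.1 describes anthracyclines as "routinely used in the treatment of breast cancer and haematological malignancies", and section 3.4 says of one referring site "The centre provides non-surgical cancer care for blood cancers and solid tumours". Figure 1 in section 3.6.1 includes a late-onset group, and section 1.1.1 notes "Late-onset cardiotoxicity is often a complication observed in childhood cancer survivors".

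**The concern.** The design rests on one assumption: that the genome in the dish is the genome of the person whose heart was assessed. Blood is a convenient source, but it is the tissue for which that assumption fails after an allogeneic transplant. The heart, and so the case or control label, belongs to the participant, while the blood cells derive from someone else.

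A transplanted case would supply cardiomyocytes from a person whose response to doxorubicin is unknown. A transplanted control would do the same. Either line could be well made and pass as a good cardiomyocyte line, yet say nothing about why this participant did or did not develop cardiotoxicity. That bears on the primary outcome and on the search for a case-specific signature and biomarkers. With at most 12 participants, a single such line carries weight.

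**Working it through.** **Step 1. Can such a participant enter?** Take a person given doxorubicin in the past, later transplanted from another person, now off steroids, with no active immunological disease and no recent infection or surgery. Sections 4.2.1 and 4.2.2 admit this person according to ventricular function, and nothing in 4.3 stops entry. Admission is by silence: the Protocol never mentions transplant.

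**Step 2. Would a planned check catch the line?**

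| Check | Section | What it tests | Shows a transplant donor's genome? |
|---|---|---|---|
| Microscopy | 6.2.2.3 | Morphology, efficiency, cell health | No |
| PCR | 6.2.2.4 | Residual vector, pluripotency genes | No |
| Karyotyping | 6.2.2.5 | Chromosome complement | Only if the sexes differ; no acceptance rule or action stated |
| Immunocytochemistry | 6.2.2.6 | Stem-cell and cardiac markers | No |
| Electrophysiology | 6.2.2.8 | Electrical and calcium behaviour | No |
| Withdrawal for an unusable sample | 4.4 | Undefined, discretionary | Not by itself; donor-derived blood need not look unusable |

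Comparing a line with stored mononuclear-cell DNA would not help either, because after a complete graft both come from the transplant donor.

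**Step 3. Does matching help?** Section 3.5.1 matches on tumour type, age and treatment regime. None of these restores the identity of a line.

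**Step 4. Size, for illustration only.** The Protocol has no figure to reproduce. Section 3.6.1 sets a maximum of 12 on pilot and financial grounds, without alpha, power, effect size or SD. The group split is in a figure not shown.

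Assumptions: 6 v 6, SD 1, two-sided 5% t test, and a mislabelled case line that behaves like a control. With k such lines among 6 cases and a true difference δ, the expected difference is δ × (6 − k)/6.

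- k = 1: δ × 5/6, a loss of 1/6 (17%).
- k = 2: δ × 4/6, a loss of 2/6 (33%).

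Power, from the noncentral t distribution for the clean designs and from 200,000 simulated trials for the mislabelled one:

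| δ (SD) | 6 v 6, all correct | 6 v 6, one case mislabelled | 5 v 6, that person not enrolled |
|---|---|---|---|
| 1.0 | 0.35 | 0.23 | 0.32 |
| 1.5 | 0.65 | 0.43 | 0.60 |
| 2.0 | 0.88 | 0.63 | 0.84 |

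Under these assumptions, including the person costs more than losing one case.

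**Step 5. How likely is it?** The documents give no share of affected patients. For an assumed share q, the chance of at least one among 12 is 1 − (1 − q)^12. If karyotyping flagged the other-sex half (also assumed), q/2 replaces q for an undetected case.

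| Assumed q | At least one | At least one undetected |
|---|---|---|
| 0 | 0 | 0 |
| 2% | 0.215 | 0.114 |
| 5% | 0.460 | 0.262 |
| 10% | 0.718 | 0.460 |
| 20% | 0.931 | 0.718 |

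**The case against.** The strongest reply is that the affected group may be empty. The mention of blood cancers in section 1.1 is general background, section 3.4 describes the whole service of one site, and section 1.1.1 speaks of childhood cancer survivors without naming blood cancer or transplant. Section 3.6.2 has experienced clinicians choose participants purposively. The exclusions for steroids, immunological disease and recent infection will remove some transplanted patients. The study is a pilot that claims no power. All of this stands, and it limits the weight of the point. It does not close the gap, because nothing tells the selecting clinician that transplant history invalidates a line, and a long-term survivor off steroids passes.

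A reader might also infer more than the documents support:

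- *That every transplanted patient is a problem.* After an autologous transplant the blood is still the participant's own.
- *That a line from a malignant clone is also mislabelled.* It keeps the participant's germline and clinical label. Its fault is acquired tumour changes that could be read as constitutional biology. Matching on tumour type may partly balance these between groups.
- *That the error is invisible to quality control.* Karyotyping could show a donor of the other sex or gross clonal change.
- *That the Protocol plans to recruit blood-cancer patients, or that 17% is an estimate of bias.* The first is inferred from background and site descriptions. The second depends on the assumptions in Step 4.
- *That all blood cancer outside remission should be excluded.* Sections 4.2.1 and 4.2.2 expressly admit people still receiving doxorubicin, so that exclusion would cut into the intended population and is debatable.

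**Conclusion.** The point holds for prior allogeneic transplant. Eligibility is silent on it, blood is the only cell source, and no planned check ties a line to the participant's genotype. A line with the transplant donor's genome could therefore enter the group comparison under the participant's label and undermine the primary outcome for that participant. Karyotyping is a partial safeguard with no consequence attached.

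The size is unknown: zero if no transplanted patient is enrolled, and 1/6 of the expected difference per affected case line under the 6 v 6 illustration. No figure in the Protocol is contradicted. Eligibility is protocol content, so a separate analysis plan would not settle it. This is a cheap and worthwhile correction, not evidence that the study is invalid.

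The malignant-clone issue is secondary. It concerns contamination of the biology, not a wrong label.

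**What to change.** Add one line to section 4.3, for both cohorts: *Previous allogeneic haematopoietic stem-cell transplant*, checked from the clinical record at screening. It needs no new procedure. The cost is a somewhat smaller eligible pool. The documents do not say by how much, and the roughly 30 monthly referrals in section 3.4 are all cardio-oncology referrals, not only eligible doxorubicin patients.

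For the secondary point, choose one of two rules and write it down: either do not take the research sample while circulating malignant disease is documented, or flag lines from such participants and leave them out in a sensitivity analysis. The first may delay or lose some participants. The second keeps them but reduces an already small comparison.

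It would also help to state in section 6.2.2.5 what karyotype result makes a line unacceptable, and what happens to it then.

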4.2.2 Non-cardiotoxicity Cohort

- Over 16 years of age at the time of consent.
- Capable of providing informed consent as determined by the consenting clinician.
- Receiving doxorubicin chemotherapy treatment at the time of consent or previously received doxorubicin chemotherapy treatment prior to consent.
- Normal left ventricular systolic function at the time of consent secondary to receiving doxorubicin chemotherapy treatment as determined by the clinical team.

4.3 EXCLUSION CRITERIA

- Under 16 years of age at the time of consent.
- Lacking ability to provide informed consent as determined by the consenting clinician.
- Judged to have been coerced to consent as determined by the consenting clinician.
- Pre-existing left ventricular systolic dysfunction to be reviewed by the clinical team on a case-by-
- case basis.
- Recent surgery (<3 months).
- Excessive alcohol consumption (>30 units a week) and/or recreational drug use.
- Active immunological disease as determined by the clinical team.
- On current steroid therapy with the exception of corticosteroid inhaler <2mg/kg.
- Active or recent (<6 weeks) serious infection as determined by the consenting clinician.
- Inability to comply with study procedures.

Version 2.24. Date: 1517/095/2022; IRAS:

Page 27 of 44

Formatted: Body Text, Space Before: 0 pt, No bullets or numbering, Tab stops: Not at 1.45 cm + 1.45 cm

4.4 WITHDRAWAL CRITERIA

Participants may be withdrawn from the study if blood samples are unattainable or are unsuitable for laboratory analysis. Participants may withdraw consent to take part in the study at any time and their routine clinical care will continue unaffected and without prejudice. If a participant who has given informed consent loses capacity to consent during the study, the participant would be withdrawn from the study. Identifiable data or samples already collected with consent would continue to be retained and used in the study and participants will be made aware of this at the time of consent. Nofurther data or samples will be collected, or any other research procedures carried out on or in relationto the participant following withdrawal from the study.

54 ADVERSE EVENTS

5.1 DEFINITIONS

Adverse Event (AE): any untoward medical occurrence in a patient or clinical study subject

Serious Adverse Event (SAE): any untoward and unexpected medical occurrence or effect that:

- Results in death
- Is life-threatening
- Requires hospitalisation, or prolongation of existing inpatients' hospitalisation
- Results in persistent or significant disability or incapacity
- Is a congenital anomaly or birth defect

Medical judgement should be exercised in deciding whether an AE is serious in other situations. Important AEs that are not immediately life-threatening or do not result in death or hospitalisation but may jeopardise the subject or may require intervention to prevent one of the other outcomes listed in the definition above, should also be considered serious.

5.2 REPORTING PROCEDURES

All adverse events should be reported. Depending on the nature of the event the reporting procedures below should be followed. Any questions concerning adverse event reporting should be directed to the CI in the first instance.

5.2.1 Non serious AEs

All such events, whether expected or not, should be recorded

5.2.2 Serious AEs

An SAE form should be completed and sent to the CI within 24 hours. However, relapse and death due to cancer or CVD, and hospitalisations for elective treatment of a pre-existing condition do not need reporting as SAEs.

All SAEs should be reported to the relevant REC where in the opinion of the CI, the event was:

- 'related', i.e. resulted from the administration of any of the research procedures; and
- 'unexpected', i.e. an event that is not listed in the protocol as an expected occurrence

Version 2.24. Date: 1517/095/2022; IRAS:

Page 28 of 44

Reports of related and unexpected SAEs should be submitted within 15 days of the CI becoming aware of the event, using the NRES SAE form for non-IMP studies. The CI must also notify the Sponsor of all SAEs.

Local investigators should report any SAEs as required by their Local Research Ethics Committee, Sponsor and/or Research & Development Office.

Contact details for reporting SAEs:

Please send SAE forms to [name]

[contact] (Mon to Fri 09.00-17.00)

Email: [contact]

65 ASSESSMENT AND FOLLOW-UP

6.1 FOLLOW UP

There will be no participant follow up for this study in a research capacity. Participants will continue to receive any routine clinical follow-up independently and unrelated to this study.

6.2 DATA ANALYSIS

6.2.1 Clinical data analysis

Patient demographics and clinical test results will be recorded by the clinical team for the purposes of the study and will be accessible to the clinical team only. A list of the relevant clinical data that will be collected can be found in Appendix 13.1.3. Access to patient records to identify potential participants and check whether they meet the relevant inclusion criteria will be restricted to the patient's existing clinical care team only - which in all cases will be one of the three named co-investigators on page 8 of this document or, on occasion and at their discretion, their appointed research nurse.

